#### 17.5.6.1. Derivation

See section 17.5.5.1 for details on how to derive this outcome.

#### 17.5.6.2. Analysis

This outcome will be analysed as describe in section 17.4.6.2, the two-way table will be allocated treatment group by whether the infant died during after PICU stay and before 90 days post randomisation (which will be established as described in section 17.5.5.1) and the relative risk will be of death occurring.

## 18. Missing data and withdrawals

Missing data will be quantified for all outcomes presented in the final analysis report. Where known, reasons for missingness will be given.

Withdrawals from trial will be summarised and presented as line listings detailing:

- 1. Site
- 2. Time from randomisation to withdrawal
- 3. Decision to withdraw participant made by:
  - a. Clinician
  - b. Parent/person with parental responsibility
  - c. Both clinician and parent/person with parental responsibility
- 4. Reason for withdrawal:
  - a. Death
  - b. Lost to follow-up
  - c. Transfer to non-participating site
  - d. Withdrawal of consent for follow-up
  - e. Other (specify)

Every effort will be made to collect follow-up data even in the event of participants discontinuing the trial intervention. In the case of withdrawals from study, available data will still be included using an intent-to-treat approach.

#### 19. Additional analyses Additional analysis 1

A sensitivity analysis of the primary analysis will be done to assess the robustness of the primary analysis. This will be done using a Cox proportional hazards model and will allow the censoring of patients who do not observe the primary endpoint of successful extubation. The start-point and end point for patients having the event of successful extubation will be the same as those defined in section 17.4.1.1. For patients who do not have a successful extubation recorded these will be censored at the last date and time (OAODATXD) an observation is recorded on the Observations and Outcomes CRF. The cox proportional hazards model will include the allocated treatment and time on ventilation prior to randomisation as covariates.

#### Additional analysis 2

A subgroup analysis of the primary outcome will be undertaken, This was based on a recommendation from the Trial Steering Committee who met on the 20th February 2024.

The subgroup analysis will examine the primary outcome stratified by whether the baby was born prematurely or not and will include an interaction term between treatment and prematurity in the linear mixed effect model described in 18.4.1.2.

Results will be presented from the model with the interaction result alongside.

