#### 17. Efficacy Evaluations

#### 17.1. Data Sets Analysed

The principle of intention-to-treat, as far as practically possible, will be the main strategy of the analysis adopted for the primary outcome and all secondary outcomes. These analyses will be conducted on all randomised participants, in the group to which they were randomised, and for whom the outcome(s) of interest have been observed/measured. No imputations will be made.

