# 17.4.1.2. Analysis

Descriptive statistics will be presented split by treatment and overall for the time from randomisation to final successful extubation (before the data is transformed) and time off MV due to failed extubation. The summaries will be presented as median and interquartile range as the data is likely to be skewed.

A comparison of group means will be conducted using a two-sample t-test on the log transformed data (the log transformation will be done using natural logarithms). The between group difference of the log transformed data will then be back transformed by taking the exponent to give the geometric mean difference and the corresponding 95% confidence interval.

A linear mixed effects model will also be fitted on the log transformed data, using ANCOVA to test for a difference between groups with adjustment for the stratification factor of time on ventilation prior to randomisation (<24h and  $\geq$ 24h), sex and adjusted age at enrolment as a fixed effects and site as a random effect (random intercept only). The exponentiated between-group difference and corresponding 95% confidence interval will be reported.

The approach to the primary outcome analysis will be a compete case analysis and will only include those participants for which the primary endpoint has been observed. If there are any participants who have not recorded a successful extubation at the point at which they were last followed up (e.g. consent for follow up has been withdrawn) then sensitivity analysis will be conducted including these participants to assess the robustness of the primary outcome analysis.

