#### 17.4.4.2. Analysis

Summary statistics will be presented in a table for each time point (0 hours, 12, hours, 24 hours, 36 hours, 48 hours then every 24 hours while still on MV if the number of observations is  $\geq$  5 overall at the time points following 48 hours) detailing the mean and standard deviation of each of the derived measures (VI, OI and OSI) for each treatment arm and overall.

The relationship between longitudinal data for VI, OI and OSI and the event of successful extubation will be examined visually by plotting mean profile plots of longitudinal data separated by treatment group and by the time at which the final observation was observed and comparing this to the overall mean profile plot separated by treatment group.

Infants will have differing amounts of follow-up data for the outcomes VI, OI and OSI as these are recorded while on MV only. More specifically, infants who are successfully extubated earlier (and therefore completing follow-up earlier) will have less follow-up data than infants with a later successful extubation time. This will be addressed in analyses of both the longitudinal measurements (VI, OI and OSI) and the time to event outcome (time to successful extubation) using joint modelling. Joint modelling will account for the potentially informative drop-out in longitudinal measures due to successful extubation. For each measure the treatment effect will be reported together with a 95% CI and a p-value.

For the SF ratio, a repeated measures random effects model will be fitted. The dependent variable will be post baseline (0 hours) SF ratio measurements. Covariates will be: SF ratio at baseline (0 hours), treatment arm, time (fitted as a continuous variable), and the stratification factor of time on ventilation prior to randomisation (<24h and  $\geq$ 24h). Centre will be fitted as a random intercept. The treatment effect (estimated mean difference in SF ratio) will be reported together with a 95% CI and a p-value.

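### For the primary outcome, the only planned analysis that keeps infants with no recorded extubation is a Cox model, so the effect of censoring cannot be separated from the change of model and scale

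*SAP*

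**What the plan says.** SAP 17.4.1.2 sets the primary comparison: "A comparison of group means will be conducted using a two-sample t-test on the log transformed data". On the scale of the result it says: "The between group difference of the log transformed data will then be back transformed by taking the exponent to give the geometric mean difference". An exponentiated log difference is a ratio of durations. A linear mixed model on the same log scale adds prior ventilation (<24h or ≥24h), sex and adjusted age as fixed effects, with a random intercept for site.

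The analysis set is complete-case: it "will only include those participants for which the primary endpoint has been observed". SAP 17.1 adds: "No imputations will be made". If some infants have no successful extubation recorded at last follow-up, 17.4.1.2 continues, "then sensitivity analysis will be conducted including these participants to assess the robustness of the primary outcome analysis". It names no method.

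SAP 19, Additional analysis 1, supplies the method: "This will be done using a Cox proportional hazards model and will allow the censoring of patients who do not observe the primary endpoint". Censoring is at the last observation on the Observations and Outcomes form. The "model will include the allocated treatment and time on ventilation prior to randomisation as covariates"; site, sex and age are not included. The SAP gives no check of proportional hazards, no analysis on the duration scale that includes the censored infants, and no rule for reading a hazard ratio against a duration ratio.

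Extubation time is also used in 17.4.4.2, which analyses "the time to event outcome (time to successful extubation) using joint modelling". Those models address the ventilation and oxygenation indices, not the primary question.

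**The concern.** A check on how missing extubation times are handled should ideally change only that. This one also changes the effect measure, the model and the covariates. The two measures even run in opposite directions: a hazard ratio above 1 and a duration ratio below 1 both mean shorter ventilation.

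If the Cox result is weaker than the primary result, the report cannot say whether the added infants or the new model caused it. If the log-normal design model is about right and surfactant works, Cox is also the less powerful analysis, so a real effect could be described as not robust for reasons unrelated to the missing infants.

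**Working it through.** **Inputs (protocol 11.3).** Means 4.83 and 4.08 days; SD 2.5 in both arms; coefficients of variation 0.518 and 0.613; two-sided alpha 0.05; 1:1 allocation; 5% dropout. Protocol 10.2.3 gives a 1–2% likelihood of death.

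**Reproducing the plan's sample size.** For a log-normal variable, σ² = ln(1 + CV²) and μ = ln(mean) − σ²/2.

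- σ₁ = 0.487, σ₂ = 0.565; μ₁ = ln(4.289) = 1.456, μ₂ = ln(3.479) = 1.247.
- Log difference −0.2095, so the geometric mean ratio is 0.811.
- n = (z₀.₉₇₅ + z_power)²(σ₁² + σ₂²)/0.2095² = 99.5 → 100 (80% power) and 133.2 → 134 (90% power).
- 134/0.95 → 142 per group, 284 in total.

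All four figures match the protocol.

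**Is the hazard ratio constant under this model?** The hazard is h(t) = φ(z)/[σt(1 − Φ(z))], with z = (ln t − μ)/σ. At day 4 with the protocol's unequal log-SDs, z₁ = (1.386 − 1.456)/0.487 = −0.14 and z₂ = (1.386 − 1.247)/0.565 = 0.25, giving a hazard ratio (surfactant/placebo) of 1.17. Over time:

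| Day | Unequal log-SDs, ratio 0.811 | Common log-SD 0.527, ratio 0.811 |
|---|---|---|
| 1 | 6.64 | 2.78 |
| 2 | 2.05 | 1.78 |
| 4 | 1.17 | 1.36 |
| 8 | 0.94 | 1.20 |
| 14 | 0.87 | 1.14 |

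With the unequal log-SDs it crosses 1 just after day 6. With a common log-SD the geometric mean ratio equals the ratio of means, 4.08/4.83 = 0.845; at that ratio the hazard ratio is 2.26 at day 1 and 1.28 at day 4. It is not constant in any of these cases.

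**Simulated power.** 142 per arm, unadjusted models, 500 to 800 trials per setting, with 5% of infants censored at a random fraction of their true duration. The censoring pattern is an assumption. Ranges reflect separate runs; simulation error is about 1–2 points.

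| Setting | t-test and log-normal AFT | Cox |
|---|---|---|
| Unequal log-SDs, ratio 0.811 | about 90% | 57–65% |
| Common log-SD 0.53, ratio 0.811 | 90–92% | 82–84% |
| Common log-SD 0.53, ratio 0.845 | 73–75% | about 66% |

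AFT means a censored log-normal accelerated failure time model. In the two settings at ratio 0.811 it returned a duration ratio of 0.815, equal to the complete-case ratio (true value 0.811).

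**Where the disagreement comes from.** Among trials with a significant t-test at ratio 0.811:

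- Nobody censored: Cox is non-significant in about 9% (common log-SD) and 26–30% (unequal log-SDs); AFT in 0%.
- 5% censored: Cox 10% and 29%; AFT about 0.5%.

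Censoring barely moves these figures, so nearly all of the disagreement comes from the change of model.

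**How many infants are involved.** If only deaths lack an extubation time, 1–2% of 284 is about 3–6. If all planned dropout does, 284 − 2 × 134 = 16.

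**The case against.** The case for leaving the plan alone has real strength, and much of it stands.

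- A reader might infer that proportional hazards fails whenever the log-normal model holds. It does not: with no effect and equal log-SDs the hazard ratio is 1 throughout, and Cox rejected in 5.0% of simulated null trials.
- A reader might infer that the SAP assumes log-normality. It says only that the data are likely to be skewed and will be log-transformed. A t-test on logs with about 134 per arm does not need exact log-normality; the non-proportionality follows from the sample-size model.
- A reader might infer that the hazard ratio cannot be compared with the primary result at all. Magnitude and interval cannot be; direction and significance can. In one set of runs Cox and the t-test agreed in direction in at least 99% of trials.
- A ratio of 0.811 with a common log-SD is not a combination that the protocol's figures produce; the consistent pairs are 0.811 with unequal log-SDs and 0.845 with a common one. The day-1 hazard ratios also describe a period with almost no extubations. At this sample size a test of proportional hazards rejected in only about 22% of common-SD trials, though in about 70% with unequal log-SDs.
- Fitting Cox with and without the censored infants would isolate censoring on the hazard scale: 1.438 against 1.442 with 4 censored, 1.424 against 1.440 with 14. That is a workable remedy, but the SAP does not plan it and it gives no duration ratio.
- Relaxing the parametric form is a legitimate part of robustness, and a log-normal AFT cannot test log-normality. This is a reason to keep Cox, not a reason to omit a same-scale analysis.
- No decision rule depends on the Cox p-value, and the primary estimate, test and sample size are untouched.

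**Conclusion.** The point holds as a cheap improvement to a supporting analysis. The one primary-outcome analysis that retains infants without a recorded extubation alters model, scale and covariates along with the censoring, and the plan offers nothing that separates these. Under the protocol's own inputs the model change alone makes Cox miss a t-test finding in 26–30% of significant trials, or about 9% with a common log-SD at ratio 0.811. The infants at issue probably number only 3–16 of 284.

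The documents do not support the stronger reading that the Cox model is invalid and should be dropped, or that the primary result is compromised.

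The sizes rest on the log-normal design model, a non-zero treatment effect, unadjusted models and an assumed censoring pattern. The audit figures describe duration of ventilation, whereas the outcome starts at randomisation, so the hazard ratios are illustrative.

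**What to change.** In SAP 19, keep the Cox model and add a censored log-normal accelerated failure time model for the primary outcome, using the same start, end and censoring times. Fit it twice: unadjusted, to match the t-test; and with prior ventilation (<24h/≥24h), sex, adjusted age and site, to parallel the mixed model. Report each ratio of durations with its 95% CI beside the corresponding primary ratio.

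With nobody censored, the unadjusted fit returns the same point estimate as the t-test comparison, so any shift is attributable to the infants added. The adjusted fit will not match exactly unless site is handled as a random intercept; the SAP should state which form is used.

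The cost is one model in two fits and a short addition to the text. The downside is reliance on log-normality, which the new model cannot test; Cox remains for that. Like Cox, it does not resolve informative censoring such as deaths.

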11.3 Sample Size calculation

The study will be powered to detect a minimally clinically important difference of 18 hours (0.75 days) in the primary outcome variable of time of mechanical ventilation. Data are expected to be positively skewed, and will therefore be log-transformed, and resulting data back-transformed. The null hypothesis is that of no difference in time of MV between the two groups.

Data from Alder Hey Children's Hospital from an audit of 60 eligible infants admitted to PICU in the seasons 2012/3 and 2013/4 showed a mean (SD) duration of ventilation of 4.83 (2.5) days (PICANet data, 2011-14). Parameters for sample size estimation are therefore as follows:

```
E(Y_1) = 4.83 \text{ and } SD(Y_1) = 2.5 E(Y_2) = 4.08 \text{ and } SD(Y_2) = 2.5 \delta = E(Y_2)/E(Y_1) = 0.845 giving coefficients of variation: \kappa_1 = SD(Y_1)/E(Y_1) = 2.5/4.83 = 0.518 \kappa_2 = SD(Y_2)/E(Y_2) = 2.5/4.08 = 0.613
```

Using the formula of Wolfe and Carlin (1999) with r = 1 for equal allocation and a two-sided alphalevel of 0.05, sample size estimations are 100 per group for 80% power and 134 per group for 90% power.

Taking the sample size of 134 and allowing for 5% dropout requires 142 patients will be recruited to each group, giving a total of 284 participants overall.

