11.5 Analysis Plan

A full SAP will be written prior to the conduct of any comparative analysis of the treatment arms. The main features of the SAP are included here.

The primary analysis will be a test of the difference in geometric mean durations of MV between groups (placebo vs. poractant alfa), reported with the corresponding 95% confidence interval. The analysis will be conducted according to the intent-to-treat principle, and will incorporate the stratification factors of duration of ventilation (<24hrs and >=24hrs) prior to randomisation and site.

For the secondary outcomes, longitudinal data for VI, OI, OSI and SF will be analysed with joint modelling. LRSQ data will be modelled longitudinally and comparisons made between groups. Binary data will be reported in terms of relative risk with 95% confidence intervals.

Within BESS, data will be collected as to ascertain readiness for spontaneous breathing test and time of extubation.

As much information as possible will be collected about the reasons for missing outcome data; this will be used to inform any imputation approaches employed in the analysis. Such methods will be fully described in the SAP.

IRAS 220853 Page **63** of **87**

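### The Cox robustness model for duration of ventilation omits site, sex and adjusted age, so it differs from the mixed model in adjustment as well as in censoring

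*SAP*

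**What the plan says.** Randomisation is stratified by site and by prior ventilation, under or at least 24 hours (Protocol 7.3 and 11.2; SAP 8.7). Protocol 11.5 says the primary analysis "will incorporate the stratification factors of duration of ventilation (<24hrs and >=24hrs) prior to randomisation and site".

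SAP 17.4.1.2 gives two comparisons for the primary outcome. The one listed first is an unadjusted two-sample t-test on log hours. A mixed model is then fitted as well, with the prior-ventilation stratum, sex and adjusted age as fixed effects and "site as a random effect (random intercept only". The SAP does not say which of the two is primary. Both use only infants with an observed successful extubation.

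SAP section 19, Additional analysis 1, adds a Cox model to test robustness. Infants without a recorded successful extubation are kept and censored at their last recorded observation. The model "will include the allocated treatment and time on ventilation prior to randomisation as covariates". Site does not appear as a covariate, stratum or frailty, and sex and adjusted age are also absent. The sentence does not say whether prior ventilation enters as the two-level stratum or as hours.

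**The concern.** A robustness check is easiest to read when it changes one thing. This one is meant to change the handling of infants with no successful extubation, but relative to the mixed model it also changes the covariates.

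That matters more for a hazard ratio than for a ratio of geometric means. With allocation balanced within site, dropping site from a linear model of log hours leaves the expected treatment effect where it was. In a Cox model, dropping a prognostic factor moves the hazard ratio towards 1 even without confounding, because the marginal and site-conditional hazard ratios are different quantities. A Cox result weaker than the mixed model could then be put down to the censored infants when part of it comes from leaving out site.

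Few infants are likely to be censored. Protocol 10.2.3 expects deaths in 1 to 2% of severe cases, which is 3 to 6 of 284, and the 5% dropout allowance is about 14 of 284. The change the check is looking for may therefore be small.

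**Working it through.** **Planned effect, from Protocol 11.3.** The inputs are a "minimally clinically important difference of 18 hours (0.75 days"), a "mean (SD) duration of ventilation of 4.83 (2.5) days", the same SD in the treated arm (mean 4.08 days), and the formula "with r = 1 for equal allocation and a two-sided alphalevel of 0.05".

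- Log variances: ln(1 + (2.5/4.83)²) = 0.2374 and ln(1 + (2.5/4.08)²) = 0.3188; sum 0.5562; root-mean log SD √(0.5562/2) = 0.527.
- Difference in log means: ln(4.08/4.83) − ½(0.3188 − 0.2374) = −0.1688 − 0.0407 = −0.2095, a geometric mean ratio of 0.811.
- n per group = (z₀.₉₇₅ + z_power)² × 0.5562 / 0.2095². This gives 99.5, so 100, at 80% power, and 133.2, so 134, at 90%.

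These match the plan: "sample size estimations are 100 per group for 80% power and 134 per group for 90% power". Then 134/0.95 = 141.05, which agrees with "allowing for 5% dropout requires 142 patients will be recruited to each group".

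**Assumed inputs.** The documents give no between-site variance, so it is varied. Protocol section 5 gives about 14 sites. For scale, a site one SD above average has an extubation hazard e^0.3 = 1.35 times the average if the SD of the log hazard is 0.3, and e^0.5 = 1.65 times if it is 0.5.

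**Simulation 1: proportional hazards at the planned effect.** 268 infants in 14 equal sites, balanced within site and prior-ventilation stratum, Weibull times with shape π/(√6 × 0.527) = 2.43. The true hazard ratio for extubation is exp(2.43 × 0.2095) = 1.66. There were 300 replicates at SD 0 and 400 elsewhere. Both models contain treatment and prior ventilation.

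| Site SD of log hazard | HR, site omitted | HR, stratified by site | Ratio of log HRs | Power, omitted / stratified |
|---|---|---|---|---|
| 0 | 1.672 | 1.667 | 1.006 | 98.7 / 96.7% |
| 0.1 | 1.674 | 1.683 | 0.990 | 98.3 / 96.8% |
| 0.2 | 1.653 | 1.683 | 0.965 | 98.3 / 96.8% |
| 0.3 | 1.624 | 1.683 | 0.932 | 97.3 / 96.8% |
| 0.5 | 1.556 | 1.683 | 0.850 | 94.8 / 96.8% |
| 0.8 | 1.464 | 1.683 | 0.732 | 91.7 / 96.8% |

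At SD 0.3 the shift is ln(1.683/1.624) = 0.036, or 0.28 of the standard error of 0.126. At 0.5 it is ln(1.683/1.556) = 0.078, or 0.62 of a standard error. The Monte Carlo error of the paired difference in log hazard ratio is 0.003 to 0.004. The geometric mean ratio was the same with or without site to within 0.001 throughout.

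**Simulation 2: smaller hazard ratio, unequal sites, 3% censored.** True hazard ratio 1.45, 300 replicates.

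| Site SD | Shrinkage of log HR | Power, omitted / stratified |
|---|---|---|
| 0 | 1% | 86 / 80% |
| 0.2 | 3% | 83 / 80% |
| 0.3 | 7% | 83 / 82% |
| 0.5 | 15% | 80 / 86% |
| 0.7 | 22% | 73 / 84% |

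A separate run with 284 infants, Weibull shape 2 and hazard ratio 1.45 (250 replicates) gave power of 84 / 82%, 75 / 83% and 67 / 82% at SDs of 0.3, 0.5 and 0.7. The power loss at large SDs is therefore sensitive to the set-up. The shrinkage is not.

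**Simulation 3: log-normal times, the sample-size model.** Hazard ratios without and with site strata were 1.45 and 1.48 with no site effect, and 1.45 and 1.54 with 20% of the log variance between sites. The two Cox models differ slightly here even when sites are identical, because hazards are not proportional. The values near 1.45 also show that the hazard ratio in simulation 2 fits the planned effect.

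**The case against.** The case against is strong on size. A reader might infer that the hazard ratio is certain to be attenuated and that power is lost. The documents do not support that. They report no site variation in extubation, and Protocol 4.2 and 8.1.4 impose one weaning and extubation protocol on all sites in order to reduce it. If the site SD is 0.3 or less, omitting site costs no power, and stratifying by site can cost a few points. Some variation can remain, because readiness for a breathing test also rests on clinician judgement (Protocol 8.1.4; SAP 17.4.2.1), but an SD of 0.5 or more is an assumption.

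A reader might also infer that the Cox model breaks Protocol 11.5. It does not: that section commits the primary analysis to both strata, not every sensitivity analysis. Nor does the SAP call the mixed model primary. Against the t-test listed first, the Cox model adjusts for more.

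Finally, a reader might infer that adding site would make any remaining disagreement attributable to censoring. It would not. A hazard ratio and a geometric mean ratio are different measures under different assumptions and need not agree even with matched covariates.

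What stands is that site is a design stratum carried by the adjusted model, and it is dropped without a reason from the only named analysis that retains infants without a recorded extubation.

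**Conclusion.** The point holds as a low-severity inconsistency. The Cox model omits site, sex and adjusted age, so it does not match the mixed model of SAP 17.4.1.2. A difference between the two could come from adjustment, from censoring or from the change of effect measure.

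If extubation rates vary between sites, the hazard ratio may be pulled towards 1: by about 0 to 7% on the log scale for site SDs of 0 to 0.3, and about 15% at 0.5. At an SD of 0.5 the power loss was 2 points with a hazard ratio of 1.66 and 6 to 8 points with 1.45. These figures rest on assumed, normally distributed site effects and 14 sites. The effect of omitting sex and adjusted age was not simulated, nor was the frailty version.

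This is a supportive analysis. With allocation balanced within site the shift is non-collapsibility, not confounding, and it does not create false positives.

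**What to change.** In SAP section 19, Additional analysis 1, specify the Cox model with allocated treatment, the two-level prior-ventilation stratum, sex, adjusted age, and site as a shared frailty. Strata are an alternative if sites are large enough: 284 infants over about 14 sites is roughly 20 each, and some will be smaller. Make the choice before allocations are released to the analysts.

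To show what the censored infants contribute, run the same Cox model on complete cases only and report the two hazard ratios together. Both are then on one scale with one covariate set. State in 17.4.1.2 whether the t-test or the mixed model is primary, so that the reference for the check is clear.

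The cost is a few lines of SAP text and code and one extra model run. Strict stratification by site can lose a few points of power when sites barely differ (80% against 86% in simulation 2 with no site variation), which favours the frailty version.
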